10.2. Reporting period

For each participant, the safety event reporting period begins at the time of the participant's first dose of this product or the time of the participant's informed consent if he or she is receiving this product at study start, and lasts through the end of the observation period of the study, which must include at least 28 calendar days following the last administration of the product under study; a report must be submitted to Pfizer Safety (or its designated representative) for any of the types of safety events listed in the table above occurring during this period. If a participant was administered the product under study on the last day of the observation period, then the reporting period should be extended for 28 calendar days following the end of observation. Most often, the date of informed consent is the same as the date of enrollment. In some situations, there may be a lag between the dates of informed consent and enrollment. In these instances, if a participant provides informed consent but is never enrolled in the study (e.g., participant changes his/her mind about participation), the reporting period ends on the date of the decision to not enroll the participant.

If the investigator becomes aware of a SAE occurring at any time after completion of the study and he or she considers the SAE to be related to this product, the SAE also must be reported to Pfizer Safety.

10.3. Causality assessment

The investigator is required to assess and record the causal relationship. For all AEs, sufficient information should be obtained by the investigator to determine the causality of each AE. For AEs with a causal relationship to this product, follow-up by the investigator is required until the event and/or its sequelae resolve or stabilize at a level acceptable to the investigator, and Pfizer concurs with that assessment.

An investigator's causality assessment is the determination of whether there exists a reasonable possibility that this product caused or contributed to an AE. If the investigator's final determination of causality is "unknown" and he or she cannot determine whether this product caused the event, the safety event must be reported within 24 hours.

If the investigator cannot determine the etiology of the event but he or she determines that this product did not cause the event, this should be clearly documented on the CRF and the NIS AEM Report Form.

10.4. Definitions of safety events

10.4.1. Adverse events

An AE is any untoward medical occurrence in a participant administered a medicinal product. The event need not necessarily have a causal relationship with the product treatment or usage. Examples of AEs include but are not limited to:

- Abnormal test findings (see below for circumstances in which an abnormal test finding constitutes an AE);
- Clinically significant signs and symptoms;
- Changes in physical examination findings;
- Hypersensitivity;
- Progression/worsening of underlying disease;
- Lack of efficacy;
- Drug abuse;
- Drug dependency.

Additionally, for medicinal products, they may include the signs or symptoms resulting from:

- Drug overdose;
- Drug withdrawal;
- Drug misuse;
- Off-label use;
- Drug interactions;
- Extravasation;
- Exposure during pregnancy;
- Exposure during breastfeeding;
- Medication error;
- Occupational exposure.

PFIZER CONFIDENTIAL

CT24-WI-JPN-GPSP01-RF08 7.0 Non-Interventional Study Protocol Template for Primary Data Collection Study

15-Sep-2022

Page 28 of 35

Abnormal test findings

The criteria for determining whether an abnormal objective test finding should be reported as an AE are as follows:

- Test result is associated with accompanying symptoms, and/or
- Test result requires additional diagnostic testing or medical/surgical intervention, and/or
- Test result leads to a change in study dosing or discontinuation from the study, significant additional concomitant drug treatment, or other therapy, and/or
- Test result is considered to be an AE by the investigator or Pfizer.

Merely repeating an abnormal test, in the absence of any of the above conditions, does not constitute an AE. Any abnormal test result that is determined to be an error does not require reporting as an AE.

10.4.2. Serious adverse events

A SAE is any untoward medical occurrence in a participant administered a medicinal or nutritional product (including pediatric formulas) at any dose that:

- Results in death;
- Is life-threatening;
- Requires inpatient hospitalization or prolongation of hospitalization (see below for circumstances that do not constitute AEs);
- Results in persistent or significant disability/incapacity (substantial disruption of the ability to conduct normal life functions);
- Results in congenital anomaly/birth defect.

Medical and scientific judgment is exercised in determining whether an event is an important medical event. An important medical event may not be immediately life-threatening and/or result in death or hospitalization. However, if it is determined that the event may jeopardize the participant or may require intervention to prevent one of the other outcomes listed in the definition above, the important medical event should be reported as serious.

Examples of such events are intensive treatment in an emergency room or at home for allergic bronchospasm; blood dyscrasias or convulsions that do not result in hospitalization; or development of drug dependency or drug abuse.

Additionally, any suspected transmission via a Pfizer product of an infectious agent, pathogenic or non-pathogenic, is considered serious. The event may be suspected from clinical symptoms or laboratory findings indicating an infection in a participant exposed to a Pfizer product. The terms "suspected transmission" and

PFIZER CONFIDENTIAL

CT24-WI-JPN-GPSP01-RF08 7.0 Non-Interventional Study Protocol Template for Primary Data Collection Study

15-Sep-2022

Page 29 of 35

“transmission” are considered synonymous. These cases are considered unexpected and handled as serious expedited cases by pharmacovigilance (PV) personnel. Such cases are also considered for reporting as product defects, if appropriate.

Hospitalization

Hospitalization is defined as any initial admission (even if less than 24 hours) to a hospital or equivalent healthcare facility or any prolongation to an existing admission. Admission also includes transfer within the hospital to an acute/intensive care unit (e.g., from the psychiatric wing to a medical floor, medical floor to a coronary care unit, neurological floor to a tuberculosis unit). An emergency room visit does not necessarily constitute a hospitalization; however, an event leading to an emergency room visit should be assessed for medical importance.

Hospitalization in the absence of a medical AE is not in itself an AE and is not reportable. For example, the following reports of hospitalization without a medical AE are not to be reported.

- Social admission (e.g., vaccinated individual/participant has no place to sleep)
- Administrative admission (e.g., for yearly exam)
- Optional admission not associated with a precipitating medical AE (e.g., for elective cosmetic surgery)
- Hospitalization for observation without a medical AE
- Admission for treatment of a pre-existing condition not associated with the development of a new AE or with a worsening of the pre-existing condition (e.g., for work-up of persistent pre-treatment lab abnormality)

10.4.3. Scenarios necessitating reporting to Pfizer Safety within 24 hours

Scenarios involving exposure during pregnancy, exposure during breastfeeding, medication error, overdose, misuse, extravasation, lack of efficacy, and occupational exposure are described below.

Exposure during pregnancy

Exposure during breastfeeding

Scenarios of exposure during breastfeeding must be reported, irrespective of the presence of an associated AE. An exposure during breastfeeding report is not created when a Pfizer drug specifically approved for use in breastfeeding women (e.g., vitamins) is administered in accord with authorized use. However, if the infant experiences an AE associated with such a drug’s administration, the AE is reported together with the exposure during breastfeeding.

Medication error

A medication error is any unintentional error in the prescribing, dispensing, or administration of a medicinal product that may cause or lead to inappropriate medication use or participant harm while in the control of the health care professional, participant, or consumer. Such events may be related to professional practice, health care products, procedures, and systems including: prescribing; order communication; product labeling, packaging, and nomenclature; compounding; dispensing; distribution; administration; education; monitoring; and use.

Medication errors include:

- Near misses, involving or not involving a participant directly (e.g., inadvertent/erroneous administration, which is the accidental use of a product outside of labeling or prescription on the part of the healthcare provider or the participant/consumer);
- Confusion with regard to invented name (e.g., trade name; brand name).

The investigator must submit the following medication errors to Pfizer, irrespective of the presence of an associated AE/SAE:

- Medication errors involving participant exposure to the product, whether or not the medication error is accompanied by an AE.
- Medication errors that do not involve a participant directly (e.g., potential medication errors or near misses). When a medication error does not involve participant exposure to the product, the following minimum criteria constitute a medication error report:
 - An identifiable reporter;
 - A suspect product;
 - The event medication error.

Overdose, misuse, extravasation

Reports of overdose, misuse, and extravasation associated with the use of a Pfizer product are reported to Pfizer by the investigator, irrespective of the presence of an associated AE/SAE.

Lack of efficacy

Reports of lack of efficacy of a Pfizer product are reported to Pfizer by the investigator, irrespective of the presence of an associated AE/SAE or the indication for use of the Pfizer product.

Occupational exposure

Reports of occupational exposure to a Pfizer product are reported to Pfizer by the investigator, irrespective of the presence of an associated AE/SAE.

PFIZER CONFIDENTIAL

CT24-WI-JPN-GPSP01-RF08 7.0 Non-Interventional Study Protocol Template for Primary Data Collection Study

15-Sep-2022

Page 31 of 35

11. SINGLE REFERENCE SAFETY DOCUMENT

In this study, the package insert of this product in Japan will serve as the Single Reference Safety Document. This document will be used by Pfizer Safety to assess any safety events reported to Pfizer Safety by the investigator during the course of this study.

The single reference safety document should be used by the investigator for prescribing purposes and guidance.

12. PLANS FOR DISSEMINATING AND COMMUNICATING STUDY RESULTS

Information collected in this study will be used for reporting purposes to report Ministry of Health, Labour and Welfare (MHLW), Pharmaceuticals and Medical Devices Agency (PMDA), Pfizer Inc. which is the corporate parent of the sponsor of this study, and the group companies, or regulatory agency in other countries. Also, it will be used for submitting application of reexamination (including Periodic Safety Update Report) or re-evaluation, preparation of material for proper use information of this product, publications, or activities for information provision. In addition, Pfizer may publish the study results to provide information for proper use, as needed, on www.clinicaltrials.gov (ClinicalTrials.gov), as presentations at academic conferences, or as manuscripts, etc.

Data obtained from the participants registered in this study will be reported to the MHLW pursuant to the Pharmaceutical and Medical Device Act. In this case, the data may be publicly posted in MHLW's "Pharmaceutical and Medical Device Safety Information" and "Pharmaceuticals and Medical Devices Information Website (<http://www.info.pmda.go.jp>)" as a listing of participants, which will include the names of drugs, adverse reactions, gender, age (increment of 10 years), and other relevant information. Furthermore, data collected may also be disclosed if the MHLW is required to disclose such information in accordance with the "Act on Access to Information Held by Administrative Organs" (Law No. 42 dated May 14, 1999); provided that in no event will the names of physicians, medical institutions, and other personal information be participant to such disclosure, nor will it be posted or disclosed.

In the event of any prohibition or restriction imposed (e.g., clinical hold) by an applicable Competent Authority in any area of the world, or if the investigator is aware of any new information which might influence the evaluation of the benefits and risks of a Pfizer product, Pfizer should be informed immediately.

In addition, the investigator will inform Pfizer immediately of any urgent safety measures taken by the investigator to protect the study participants against any immediate hazard, and of any serious breaches of this NI study full protocol that the investigator becomes aware of.

16. OTHER NECESSARY MATTERS

1. Amendment of the Full Protocol

Based on the new knowledge to be obtained according to the progress of this study, the need for amendment of the protocol will be examined and the Full Protocol will be amended if necessary. Also, the need for amendment of the Full Protocol will be examined and the protocol will be amended when the partial change in the dosage and administration or indication is approved during the reexamination period (except when the reexamination period is newly designated), etc.

2. Actions to be taken for any problem or issue

Revision of the package insert and conduct of a new Post-marketing study or new Post-marketing clinical trial should be considered for the following cases: any serious and unknown adverse reaction is suggested; a significant increase in the frequency of adverse reactions is noted; any effectiveness or safety concern compared to pre-approval is raised; rare adverse reaction is suggested.

APPENDIX 1. LIST OF STAND ALONE DOCUMENTS

Not applicable.

1. REVISION HISTORY

Version/ Date/ Author(s)/ Status of Study	Summary of Changes/Comments
1.0 08-DEC-2023 PPD Before Enrollment	First edition
2.0 14-JUN-2024 PPD Enrollment Complete	
 • Section 8.2.1.1 Changed the participants included in the analyses from “CRF-collected participants” to “CRF-fixed participants” and deleted the analyses of CRF-uncollected participants. • Section 8.2.2.2 Added summarization of the dose interval between the initial immunization (third vaccination) and the fourth vaccination. • Section 8.2.3.5 Deleted the subgroup analysis regarding serious adverse events from the plan because it was an erroneous description.

2. INTRODUCTION

This document describes the statistical analysis plan for the special investigation of COMIRNATY Intramuscular Injection for 6 months to 4 years old (monovalent: Omicron XBB.1.5) (hereinafter referred to as this product). In this SAP, citations from the corresponding protocol are indicated in *italics*.

2.1. Study Objective

To collect information on adverse events, reactogenicity events (local reactions and systemic reactions), and COVID-19 that occur subsequent to the fourth vaccination with this product in children aged 6 months to 4 years who received the first booster immunization with this product (fourth vaccination with this product) after the initial immunization under actual use, and to confirm its safety in the early stage.

2.2. Study Design

2.2.1. Setting

Vaccinated participants must meet all of the following criteria to be eligible for inclusion in the study.

- *Participants who are 6 months to 4 years old at the time of the fourth vaccination with this product.*

- *Participants who are receiving the first booster immunization with this product (fourth vaccination with this product) after the initial immunization.*
- *Participants for whom written consent was obtained from their legally acceptable representatives (parents or legal guardians) regarding their participation in the study upon understanding the explanatory document describing the content of this study, including that they will be asked to record participant's symptoms in the health observation diary.*

2.2.2. Exclusion criteria

There are no exclusion criteria for this study.

2.2.3. Method of administration

[Indications]

Prevention of infection with SARS-CoV-2

[Dosage and administration]

This product is diluted with 2.2 mL of Japanese Pharmacopoeia physiological saline. For initial immunization, participants are vaccinated intramuscularly at a dose of 0.2 mL 3 times in total. The second dose is usually given at a 3-week interval, and the third dose is given after at least 8 weeks have passed since the second vaccination. For booster immunization, participants are vaccinated intramuscularly at a dose of 0.2 mL.

[Precautions regarding dosage and administration (booster immunization)]

Participants: Those aged 6 months to 4 years with a history of previous vaccination with SARS-CoV-2 vaccines for initial immunization or booster immunization. Based on the state of SARS-CoV-2 pandemic and individual background factors, etc., the necessity of booster immunization should be determined in consideration of benefits and risks.

Vaccination interval: Generally, participants can receive vaccination after at least 3 months have passed since the previous SARS-CoV-2 vaccination.

2.2.4. Observation period

The observation period will be from the date of the fourth vaccination with this product (Day 1) to 28 days after the fourth vaccination. However, for those who withdraw from the study, information up to the time of withdrawal will be collected.

2.2.5. Tabulation period

The tabulation period will be the same as the observation period.

2.2.6. Safety specifications

[Important identified risks]

- *Shock, anaphylaxis*
- *Myocarditis, pericarditis*

[Important potential risks]

- *Vaccine-associated enhanced disease (VAED) and vaccine-associated enhanced respiratory disease (VAERD)*
- *Guillain-Barre syndrome*

2.2.7. Planned sample size and its rationale

60 participants will be collected as the participants to be included in the safety analysis set.

The target sample size (safety analysis set) was set to be 60 participants based on feasibility. If 60 participants can be collected, an adverse event that occurs with a true incidence of 3% can be observed in at least 1 participant with a probability of 83%, which would make it possible to understand trends in incidence of reactogenicity events.

3. INTERIM AND FINAL ANALYSES

In this study, interim analyses for Japan Periodic Safety Update Report (J-PSUR) will be conducted on a regular basis. At the time of an interim analysis, only necessary items for J-PSUR selected from the full analysis items defined in this SAP will be analyzed. A final analysis will be conducted to support the application of reexamination. At the time of final analysis, the full items defined in this SAP will be analyzed.

4. HYPOTHESES AND DECISION RULES

Because of the non-confirmatory nature of this study, no hypothesis tests will be performed.

4.1. Statistical Hypotheses

No hypothesis tests will be performed.

4.2. Statistical Decision Rules

Not applicable.

5. ANALYSIS SETS

5.1. Safety Analysis Set

The safety analysis set is the full analysis set that is as close to all participants who have received the fourth vaccination with this product as possible. Specifically, the safety analysis set consists of all participants who have been registered or reported in this study except those who meet at least one or more following conditions:

1. No case report form is collected. (Indicated as “CRF not collected” in the study report.)
2. Any violation or deficiency is found concerning the study contract. (Indicated as “Contract violation/deficiency” in the study report.)
3. The registration does not meet all the requirements. (Indicated as “Invalid registration” in the study report.)
4. No information is reported for the inoculation of the target vaccine (Indicated as “No information on inoculation” in the study report)
5. No information is reported for adverse events. – No report after the fourth vaccination (Indicated as “No AE information” in the study report.)

Details of each criterion follow the latest Guidance for Adoption/Rejection Criteria for Analysis Populations and Handling of Data in Drug Use-Results Surveys.

5.2. Effectiveness Analysis Set

Not applicable.

5.3. Other Analysis Sets

Not applicable.

5.4. Subgroups

Subgroup analyses of safety will be performed with respect to the following vaccinated participant characteristics (factors):

- Sex [male, female]
- Age at the fourth vaccination [6 months to <2 years, 2 years to ≤4 years]
- Past history of allergy [absent, present]
- Past history of SARS-CoV-2 infection [absent, present]

In addition, subgroup analyses of safety with respect to other factors indicated below will be performed, as necessary:

- Hepatic impairment [absent, present]
- Renal impairment [absent, present]
- History of other vaccination (before and after vaccination with this product) [absent, present]

Presence/absence of renal/hepatic impairment should be determined according to "Attachment: Procedure to Extract Patients with Hepatic/Renal Impairment in Post-Marketing Surveillances."

6. ENDPOINTS AND COVARIATES

6.1. Safety Endpoints

- Adverse reactions: Adverse events considered by the physician to be causally related
- Adverse event: Any untoward and unintended sign or symptom occurring after vaccination with this product, regardless of causal relationship
- Serious adverse events or adverse reactions: Adverse events or reactions considered by the physician to be serious
- Reactogenicity events: Local and systemic reactions collected in the health observation diary
- Safety specifications: Important identified risks, important potential risks, and important missing information described in the Risk Management Plan. The safety specifications to be investigated in this study are listed below.

[Important identified risks]

- *Shock, anaphylaxis*
- *Myocarditis, pericarditis*

[Important potential risks]

- *Vaccine-associated enhanced disease (VAED) and vaccine-associated enhanced respiratory disease (VAERD)*
- *Guillain-Barre syndrome*

The definition of each safety specification event will be based on the definitions in the Risk Management Plan or Periodic Benefit-Risk Evaluation Report (PBRER) as of the database release (or J-PSUR due date).

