8.7.2. Safety analysis

The events entered in the CRF submitted by the investigator for which the causal relationship with this product cannot be ruled out will be handled as adverse reactions, and the number and proportion of participants with adverse reactions ([%]: number of participants with adverse reactions/number of participants included in safety analysis) will be tabulated. Exploratory analyses will be performed as needed.

8.7.3. Analysis of reactogenicity events (local reactions and systemic reactions [health observation diary])

Local reactions and systemic reactions recorded in the health observation diary collected by the investigator from study participants will be handled as reactogenicity events, and the number and proportion of participants with each event will be tabulated. Exploratory analyses will be performed as needed.

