7. HANDLING OF MISSING DATA

If the seriousness of an adverse event, action taken for an adverse event, or outcome of an adverse event is missing, the event will be treated as having a value of "unknown" for data tabulation. If the causality of an adverse event is missing, the event will be treated as "causally related" for data tabulation.

Cleaning-uncompleted data will be in principle handled as follows:

- Items for which relevant data are missing: For both tabulation and listing, their values will be handled as missing data (or they will be treated as "unknown" for a categorical variable).
- Items for which relevant data are inconsistent: For both tabulation and listing, their values will be handled as missing data. In addition, a list will be presented separately for details of data-handling.
- Items with no signature: For both tabulation and listing, any record in a CRF with no signature of a contract physician (including when the CRF is signed only by individuals other than contract physicians) will be handled as missing data.

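### SAP 6.1 defines adverse reactions more narrowly than protocol 8.7.2, so an event with causality recorded as *unknown* would count under one rule and not the other

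*SAP*

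**What the plan says.** Protocol 8.7.2 sets the rule for the main safety tabulation. Events entered in the CRF "for which the causal relationship with this product cannot be ruled out will be handled as adverse reactions", and the number and proportion of children with such reactions are tabulated over the safety analysis population.

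SAP 6.1 words the endpoint differently: "Adverse reactions: Adverse events considered by the physician to be causally related".

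Protocol 10.3 describes the investigator's judgement as "the determination of whether there exists a reasonable possibility that this product caused or contributed to an AE". It also provides for a final determination of *unknown*, where "he or she cannot determine whether this product caused the event", and requires such an event to be reported within 24 hours. The next paragraph deals separately with an event of undetermined etiology that the investigator nevertheless decides the product did not cause.

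SAP 7 has one sentence specific to causality: "If the causality of an adverse event is missing, the event will be treated as" causally related. It has no sentence for a causality entered as *unknown*. Protocol 8.3.8 lists causal relationship among the items to be recorded but gives no answer categories.

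**The concern.** One rule leaves out only events for which the product has been excluded as a cause. The other takes in only events for which it has been affirmed. They agree unless an event falls between the two, and protocol 10.3 names such a case.

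The SAP definition feeds the overall, serious and detailed adverse-reaction tables (SAP 8.2.3.1.1 to 8.2.3.1.3), the table for children excluded from the safety analysis set (8.2.3.1.5) and the adverse-reaction part of the subgroup analyses (8.2.3.5). SAP 3 plans interim analyses for the periodic safety report as well as a final analysis, so the count has to be made the same way each time. Protocol 16 lists a significant increase in the frequency of adverse reactions among the grounds for considering a package insert revision or a new study. If the two rules give different counts, the SAP's is the lower.

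**Working it through.** **The plan's own figure.** The only design figure is the chance of seeing at least one event of 3% true incidence among 60 children: 1 − 0.97^60 = 0.839, against 83% stated in protocol 8.5.2 and SAP 2.2.7. It is reproduced closely enough, and nothing below depends on it.

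**Each possible causality entry under each rule.**

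| Causality entry | Protocol 8.7.2 | SAP 6.1, read literally, with SAP 7 |
|---|---|---|
| Related | counts | counts |
| Not related | does not count | does not count |
| Missing | not excluded, so counts | counts (SAP 7 causality sentence) |
| *Unknown* | not excluded, so counts | does not count; SAP 7 has no rule |

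Only the last row differs. Under the literal SAP reading, an empty field is counted as a reaction and a physician's recorded uncertainty is not. SAP 8.2.3.1.1 to 8.2.3.1.3 and 8.2.3.5 add no rule that would close the gap.

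**Size.** Inputs: n = 60, the target safety analysis set (protocol 8.5.1); k = the number of children who have an event of *unknown* causality and no event that is related or has missing causality. The documents give no value for k.

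Protocol proportion − SAP proportion = k/n.

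- k = 0: 0 points
- k = 1: 1/60 = 1.7 points
- k = 2: 2/60 = 3.3 points
- k = 3: 3/60 = 5.0 points

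These values of k are assumptions to show the range, not estimates. Registration may continue beyond 60 (protocol 8.2.4). At assumed sizes of 80 and 100 the shift per child would be 1/80 = 1.25 and 1/100 = 1.0 points. The difference cannot be negative, because every event that counts under the literal SAP reading also counts under the protocol.

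**The case against.** The strongest reply is that no difference in counts has been shown. The gap opens only if *unknown* can be recorded on the CRF, and the answer categories are not in the documents. If the item offers only related and not related, judged on the reasonable-possibility standard, the two counts may coincide. The *unknown* sentence in protocol 10.3 concerns expedited reporting and does not define a tabulation category. The same section says that "sufficient information should be obtained by the investigator to determine the causality of each AE", so *unknown* should be uncommon. **This stands.** It makes the effect conditional, but it does not remove the difference in wording.

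A second reply is that protocol 8.7.2 already covers *unknown* and the SAP never withdraws it, so an analyst reading both documents would count the event. That is the sensible reading, but it means setting aside the literal definition in SAP 6.1. Protocol 8.7 also allows the SAP to modify the protocol's plans, so the narrower wording could be intended. Neither document says it is. The SAP revision history does not mention it, though version 1.0 is logged only as a first edition, so that silence proves nothing either way.

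A third reply is that little is lost. Symptoms specified in the diary are recorded separately from physician-evaluated adverse events, no hypothesis test or decision rule uses the proportion, and the events stay visible. Serious ones are tabulated under SAP 8.2.3.2.1, non-serious ones under 8.2.3.2.2 (where an incidence threshold may apply), and all appear in the SAP 9 listing. **This also stands**, and it keeps the point minor.

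Two stronger readings should not be drawn:

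- A reader might infer that SAP 7 contradicts itself, because it treats missing causality as related but elsewhere turns missing categorical items into *unknown*. The latter bullet covers only data whose cleaning is incomplete, and only in principle. The specific causality sentence is naturally taken to govern.
- A reader might attach exact confidence intervals to the shift: the upper 95% limit is 6.0% for 0/60 and 8.9% for 1/60. SAP 8.1.3 gives the method only for cases where an interval is determined, and the adverse-reaction tables specify n and proportion alone. Those limits do not describe a planned output.

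**Conclusion.** The point holds as a conflict of wording with a conditional effect. Protocol 8.7.2 and SAP 6.1 state different rules for the same proportion, and they give different answers for an event whose final causality is *unknown*. If the CRF allows that entry and SAP 6.1 is applied literally, the reported proportion is lower than the protocol's by 1.7 points per affected child at n = 60. If the entry is not available or never used, the effect is zero.

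A reader might infer that adverse reactions will be under-reported. The documents do not support that: they give neither the answer categories nor any number of affected children, and no adverse event drops out of the listing.

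Severity is minor. Confidence is high for the wording conflict and moderate for any effect on the counts.

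**What to change.** In SAP 6.1, replace the definition with the rule in protocol 8.7.2. In SAP 7, extend the causality sentence so that it covers a causality that is missing or unknown, with both tabulated as causally related.

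If the narrower definition is what the sponsor wants, say so in the SAP, record it as a deliberate change from protocol 8.7.2 and give the reason.

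The cost is one or two sentences and no new data. The downside is that the reported adverse-reaction proportion may be slightly higher, because events of undetermined cause are counted as reactions. That is the direction SAP 7 already takes for missing causality.
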